## Secondary objectives:

- 4. To provide VE estimates at day 90/180/365 (pending data distribution) after immunisation with a bivalent booster among immunocompromised individuals.
- 5. To provide VE estimates at day 365 after immunisation with a bivalent booster among females and males, and 50-69-year-olds and 70+-year-olds.
- 6. To provide VE estimates at day 365 after immunisation with a bivalent booster according to time since a previous infection.
- 7. To provide VE estimates at day 365 after immunisation with a bivalent booster according to time between-dose intervals (for both the primary course and the booster doses).
- 8. To provide VE estimates at day 365 after immunisation with a bivalent booster according to the vaccine brand received as fourth dose.

Objective #1-2 and #5-8 will be examined within our main study cohort. Objective #3 will be examined within a subpopulation of the main study cohort consisting of those hospitalized for Covid-19. Objective #4 will be examined within a secondary cohort consisting of individuals with presumed immunocompromised conditions aged  $\geq$ 18 years.

#### 9. RESEARCH METHODS

## 9.1 Study design

We will take advantage of the unique nationwide register-data available to us, and construct country cohorts with individual-level information on dates of vaccination and dates of effectiveness end-points together with relevant covariate information. All Nordic residents are assigned a unique personal identifier at time of birth or immigration, enabling linkage between registers. The four Nordic

countries have universal and tax-financed healthcare systems and reporting to national registers is mandatory, providing near-complete follow-up of all residents over time. The cohort participants will be classified according to Covid-19 vaccinations received and followed up using survival analysis. We will utilize comparative designs avoiding comparisons with unvaccinated individuals. This will reduce concern about selection bias due to inherent differences in who chooses to remain unvaccinated.

The study period will start on 1 September 2022 in Denmark, 18 July 2022 in Finland, and 1 July 2022 in Norway and Sweden. These country-specific start dates correspond to when fourth dose vaccination was offered to the general public within the respective country. The study period will end on last date of data availability at time of analyses during autumn 2023 (tentative date: 30 September 2023).

The overall research design builds on target trial emulation methodologies to infer causal relative and absolute effect estimates according to average treatment effect among treated. Key components of the specification and emulation of the pragmatic target trials of the effectiveness of the bivalent Covid-19 booster vaccines against severe Covid-19 using Nordic nationwide registry data are including in table below.

Treatment strategies	
 
Have an immunocompromised condition         (ascertained by registered diagnosis of solid         malignancy, hematologic malignancy,         rheumatologic or inflammatory disorder, other         intrinsic immune condition or immunodeficiency,         organ or stem cell transplant, or received a Covid-         19 vaccine dose equivalent of booster dose for         immunocompromised)
 
For the target trial comparing booster vs unboosted:         1) Receive a BA.1 or BA.4-5 bivalent booster         2) Do not BA.1 or BA.4-5 bivalent booster and         continue being unboosed during follow-up
 
For the target trial comparing between boosters:         1) Receive a BA.1 bivalent booster         2) Receive a BA.4-5 bivalent booster         3) Receive an original monovalent         The bivalent (or original monovalent) booster is         received as a 4th dose within the general population         (objective #1-#2, #5-#8) and as any booster (≥4th)
 
	Same as for the target trials. We define the date of booster vaccination (that is, the index date) according to the registered date of administration.
	dose for the immunocompromised population	
	(objective #4)	
Treatment assignment	Individuals are randomly assigned to a strategy at baseline in a 1:1 ratio (for immunocompromised population, conditional on number of previous doses received). Individuals will be aware of the assigned treatment strategy.	Individuals are assigned to the strategy compatible with their type of booster received; randomization is assumed conditional on matching (in a 1:1 ratio) on baseline covariates; unboosted are assigned the index data of the matched booster.
		date of the matched booster recipient.
Outcomes	Covid-19 hospitalization (ascertained by positive SARS-CoV-2 PCR test in relation to Covid-19 registered inpatient hospitalization) and Covid-19 death (ascertained by positive SARS-CoV-2 PCR test in relation to any (or Covid-19 cause-specific [in Norway]) death.	Same as for the target trials.
Follow-up	Follow-up for each individual will start at day 8 from	Same as for the target trials.
	treatment assignment (to ensure full immunisation among booster recipients) and end on day of outcome event, death, loss to follow-up, receipt of additional booster, 365 days (and 180 days for immunocompromised population) after baseline, or end of data collection, whichever occurs first.	
Causal contrast	Per-protocol	Observational analog to per-
of interest		protocol effect.
Statistical analysis	Kaplan-Meier estimator to obtain cumulative incidence for each treatment strategy during follow-up. Compare cumulative incidence across treatment strategies by risk ratios (to obtain VE) and risk differences.  Person-time since baseline will be stratified consecutive in three-months periods with the Kaplan-Meier estimator to estimate third-monthly changes in VEs; these VEs will contribute to meta-regression estimating comparative waning.	Same as for the target trial except observational analogs of perprotocol.

Subgroup analyses by sex (female/male), age ( ≥70 years), time between vaccine dose (between primary</th 	course and 3rd dose and 3rd and 4th dose; for	
general population target trial), and vaccine brand	
(Pfizer-BioNTech/Moderna).	

#### 9.2 Setting

The overall source cohort will consist of all individuals aged 18 years or older as of the country-specific start dates.

The main cohort (i.e., the general population cohort) for objective #1-3 and #5-8 will consist of individuals who:

- 1) Are aged ≥50 years in Denmark and Sweden, ≥60 in Finland, and ≥65 in Norway (country-specific age cut-off for booster recommendations)
- 2) Have a known residency within the specific country
- 3) Have received AZD1222, BNT162b2, or mRNA-1273 vaccines only (AZD1222 as part of the primary vaccination course only)
- 4) Did not receive a booster (i.e., the third or fourth vaccine dose) within 90 days after the last received vaccine dose
- 5) Did not receive the fourth dose before the country-specific start dates (as this would indicate individuals who were particularly vulnerable to severe disease or individuals with immunocompromising conditions and thus would not be representative of the target general population)
- 6) No history of Covid-19 hospitalization prior to the country-specific start dates

Objective #3 will be evaluated in secondary cohorts consisting of individuals hospitalized for Covid-19 from the main cohort.

Objective #4 will be evaluated in secondary cohorts consisting of presumed immunocompromised individuals aged  $\geq$ 18 years. Immunocompromised will be defined as fulfilling at least 1 of the conditions in the table below:

Immunocompromised condition	Definition
Solid malignancy (1)	ICD-10 codes: C00–C80 (except C44) registered within 3 years
	prior to the index date

Hematologic malignancy (2)	ICD-10 codes: C81-C86, C88, C90-C96, D46, D47, D61.0, D70.0,
	D61.2, D61.9, D71 registered within 3 years prior to the index
	date
Rheumatologic or inflammatory disorder (3)	ICD-10 codes: D86, E85 [except E85.0], G35, J67.9, L40.1, L40.5,
	L93, L94, M05-M08, M30, M31.3, M31.5, M32-M35, M46
	registered within 3 years prior to the index date
Other intrinsic immune condition or	ICD-10 codes: B20, B21, B22, B231, B232, B24, B9735, D27.9,
immunodeficiency a (4)	D61, D72.8, D80, D81 [except D81.3], D82-D84, D89 [except
	D89.2], K70.3, K70.4, K72, K74.3-K74.6 [except K74.60 and
	K74.69], N04, 0987, R18, Z21, Z992 registered within 3 years
	prior to the index date
Organ or stem cell transplant (5)	ICD-10 codes: T86 [except T86.82-T86.84, T86.89, and T86.9],
	Z94, and Z98.85 registered within 3 years prior to the index date
Received a Covid-19 vaccine dose equivalent of	Either 1) any booster dose (≥3rd dose) within 90 days of the last
booster dose for immunocompromised (6)	dose b , 2) receipt of fourth dose before the roll-out of the 4th dose
	boosters c , or 3) receipt of fifth or more vaccine dose doses prior
	to start of study period

Definitions of immunocompromised condition 1 to 5 are adapted and modified from Embi et al.(12) and Hughes et al.(13) aWe will examine data to determine whether a diagnosis of HIV (ICD-10 codes B20, B21, B22, B231, B232, B24, 0987, Z21) should be included. We do not have access to data on CD4-cell count; if HIV is very rarely occurring (which we assume), we will most likely not include these diagnosis codes in the immunocompromised definition. bCovid-19 vaccination courses in the Nordic countries for the general population has generally had time intervals of 6 months or more between boosters. cOf note, the start date for the roll-out of the fourth dose was earlier than start of the study period in Finland, Norway, and Sweden, as vulnerable and the elderly living in nursing homes were initially prioritized during Spring 2022, before the fourth dose was rolled out to the general population. The exact start date of the roll-out is to be specified in Finland, Norway, and Sweden (approximately February/March 2022), while it coincides with the start of the study period in Denmark (being 1 September 2022).

#### 9.3 Variables

#### **Exposures**

The Nordic countries implemented national vaccination campaigns against SARS-CoV-2 from December 27, 2020, providing free vaccinations to all residents. Phased distribution plans were implemented prioritising vaccination of individuals at highest risk of Covid-19 complications (nursing home residents, healthcare workers, and individuals of older age). Denmark and Norway almost exclusively used mRNA vaccines after full or partial discontinuation of AZD1222 in March 2021 due to serious but rare events of thrombosis with thrombocytopenia. The AZD1222 was similarly halted in Finland and Sweden for the younger population but continued as part of the utilized primary course schedules for the population older than 64 years. The mRNA vaccines have been predominantly used in all countries for booster vaccinations. Ad26.COV2.S has seen very limited use. The Nordic countries have vaccinated around 6 times more individuals with BNT162b2 than with mRNA-1273. Prioritized fourth dose vaccination rollouts to the vulnerable elderly and those living in nursing home

facilitieswere initiated in spring 2022 in Finland, Norway and Sweden, and has been offered more broadly to the general population since summer 2022. Fourth dose vaccination in Denmark was initiated in September 2022, coinciding with the time of the authorization of use of the bivalent boosters. Similar to previously received vaccination doses, the fourth vaccine dose has been classified according to vaccine brand and also according to whether it was a bivalent BA.1, bivalent BA.4-5, or monovalent (original) mRNA-booster vaccine.

For objective #3, we will for the 4 vs 3 dose comparison combine BA.1 and BA.4-5 bivalent boosters to increase statistical power. Depending on data availability, we will stratify this analysis by bivalent booster type.

#### Outcomes

Covid-19 hospitalisation will be defined as first inpatient hospitalisation with a registered Covid-19-related diagnosis and a positive PCR test for SARS-CoV-2 (within 14 days before to 2 days after the day of admission). We will define Covid-19 death as death within 30 days of a positive PCR test for SARS-CoV-2 in Denmark, Finland, Sweden, while we in Norway it will be defined as death with Covid-19-specific diagnosis registered as the main or contributary cause of death (owing to data availability). In the table below, we provide further details.

Outcome variable	Country	Data source and details
Covid-19 hospitalisation Norw	Denmark	The National Patient Register and the Danish Microbiology Database. Defined as a hospitalisation with a PCR positive test for SARS-CoV-2 within 14 days before to 2 days after the admission date, b) inpatient contact or at least 12 hours of contact, and c) a Covid-19 relevant diagnosis code (ICD-10: B342, B342A, B948A, B972, B972A, B972B, B972B1, Z038PA1)
	Finland	National Care Register for Health Care and the National Infectious Diseases Register.  Defined as a hospitalisation with a PCR positive test for SARS-CoV-2 within 14 days before to 2 days after the admission date, b) inpatient hospital contact, and c) a Covid-19 relevant main diagnosis (ICD-10: J00-J22, J46, J80-J84, J851, J86, U071, U072).
	Norway	The Norwegian Intensive Care and Pandemic Registry (NIPaR). Defined as an individual with a positive PCR test for SARS-CoV-2 who were inpatient hospitalised and where Covid-19 was registered as the main cause of hospitalisation.
	Sweden	The Swedish Patient Register and the Register on surveillance of notifiable communicable diseases (SmiNet). Defined as a hospitalisation with a PCR positive test for SARS-CoV-2 within 14 days before to 2 days after the admission date, b) inpatient contact or at least 12 hours of contact, and c) a Covid-19 relevant diagnosis code (ICD-10: U071, U072, U109)
Covid-19 death	Denmark	The Civil Registration System and the Danish Microbiology Database. Defined as (the date of) death within 30 days after PCR positive test for SARS-CoV-2.

Finland	The Finnish Population Information System and the National Infectious Diseases Register.  Defined as (the date of) death within 30 days after PCR positive test for SARS-CoV-2.
Norway	Norwegian Population Register and the Norwegian Surveillance System for Communicable Diseases (MSIS). Defined as (the date of) death with a registered ICD-10 code of U071, U072, U109, or U099 as the main or contributing cause of death.
Sweden	The Total Population Register, the Cause of Death Register, and the Swedish Patient Register and the Register on surveillance of notifiable communicable diseases (SmiNet).  Defined as (the date of) death within 30 days after PCR positive test for SARS-CoV-2.

All-cause mortality will be defined as a recording of death in the respective administrative demographic register (vital status is prospectively updated in these registers and also include information on the date of death).

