We will follow individuals from day 8 after the index date (to ensure full immunisation among booster recipients) up until the day of an outcome event, 365 days has passed since the index date (i.e., allowing up to 357 days of follow-up since day 8), receipt of additional booster, death, emigration, or end of the study period, whichever occurs first.

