### 9.8 Supplementary analyses and quality control

Quality control will be conducted indirectly to evaluate the validity of our main analyses, by 1) making sure that the prevalence of the different schedules and the number of study endpoints match national surveillance dashboards and reports, 2) descriptive and analytical results cohere to our previous findings, and 3) using a Common Data Model (CDM), by which national register data are standardised to a common structure, format and terminology in order to allow the same statistical programming scripts to be used in each country. The use of a CDM with common statistical programming scripts will facilitate efficient use of resources and reproducibility of the statistical analyses. We will ensure the scientific quality of the work, by division of review tasks (including statistical code review) and responsibilities in a timely fashion and by adhering to the ENCePP Code of Conduct (see attachment). We will perform matching quality diagnostics to assess the control of matched parameters. For the 4 vs 3 dose comparisons, we will include a sensitivity analysis where starting follow after day 21/28 after the index date for the main comparison to further reduce the potential of transient healthy vaccinee effect around the time of vaccination as well as spill-over effect (that is, prior to the index date) given that some severe Covid-19 events may take longer time to develop. Lastly, in case data do not allow for 365-day effectiveness estimation (e.g., owing to heavy censoring of matched pairs), we will, similarly to the comparison analyses among immunocompromised, use an alternative shorter length of follow-up (e.g., day 180/270).

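### Events counted from day 8 may rest on a positive PCR taken before day 8, or before the index date, and the plan addresses this only in a partial sensitivity analysis

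*Protocol*

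**What the plan says.** **Start of follow-up.** Section 9.7 (Procedures): "We will follow individuals from day 8 after the index date (to ensure full immunisation among booster recipients". Follow-up ends at the latest when "365 days has passed since the index date (i.e., allowing up to 357 days of follow-up since day 8".

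**Outcome windows.** Section 9.3 (Outcomes) requires a positive PCR for Covid-19 hospitalisation "within 14 days before to 2 days after the day of admission". Covid-19 death is "death within 30 days of a positive PCR test for SARS-CoV-2 in Denmark, Finland, Sweden". The table for those three countries dates the outcome at death: "Defined as (the date of) death within 30 days after PCR positive test for SARS-CoV-2".

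**Norway.** Death is "Defined as (the date of) death with a registered ICD-10 code of U071, U072, U109, or U099 as the main or contributing cause of death", with no PCR window. The hospitalisation row, quoted here without its last word, reads "Defined as an individual with a positive PCR test for SARS-CoV-2 who were inpatient hospitalised and where Covid-19 was registered as the main cause of". That row states no day window, but the general sentence above it gives the 14-day/2-day window without limiting it to particular countries.

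**What might screen out earlier infections.** Section 9.2 excludes only a Covid-19 hospitalisation before the country start date. The prior-infection covariate in section 9.3 uses the last positive PCR before the country's fourth-dose roll-out, not before the individual index date.

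**Safeguard.** For 4 vs 3 doses, section 9.8 plans a sensitivity analysis "starting follow after day 21/28 after the index date for the main comparison to further reduce the potential of transient healthy vaccinee effect", and also to reduce spill-over from before the index date.

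**The concern.** The day 8 start is meant to confine counting to the period of full immunisation. The rule acts on the date of admission or death, while the infection behind the event is dated by its PCR, and nothing requires that PCR to fall inside follow-up. The primary estimates therefore include events from infections detected before day 8, some of them before the index date.

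Two mechanisms pull in opposite directions:

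- Infections detected on days 0-7 fall, by the protocol's own premise, before full immunisation. If they are spread equally over the arms, they pull VE toward zero.
- Infections detected just before the index date would sit mainly in the unboosted arm if infected people put off vaccination. That would raise VE.

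All such events fall in days 8-90, the first of the four intervals in the waning meta-regression (primary objective 2). Dilution in that interval would understate waning; inflation would overstate it.

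**Working it through.** **1. The plan's own figure.** 365 - 8 = 357 days, as stated. Counting both end days, days 8-365 are 358 days and days 8-90 are 83 days.

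**2. Which event days can carry an early PCR.** Inputs: start day 8 (section 9.7); look-back of 14 and 30 days (section 9.3). Earliest qualifying PCR = start day - look-back. I take the admission date as the event date for hospitalisation, which the protocol implies but does not state.

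| | Hospitalisation | Death (Denmark, Finland, Sweden) |
|---|---|---|
| Earliest PCR | 8 - 14 = day -6 | 8 - 30 = day -22 |
| Last event day with a PCR before the index date | -1 + 14 = day 13 | -1 + 30 = day 29 |
| Last event day with a PCR before day 8 | 7 + 14 = day 21 | 7 + 30 = day 37 |
| First start that clears the index date | day 14 | day 30 |
| First start that clears day 8 | day 22 | day 38 |

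**3. What the day 21/28 start leaves.**

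- *Hospitalisation:* the earliest PCR is 21 - 14 = day 7 or 28 - 14 = day 14. The index date is cleared. Day 8 is missed by one day with a day 21 start and cleared from day 22.
- *Death:* the earliest PCR is 21 - 30 = day -9 or 28 - 30 = day -2. Days 21-29 (9 days) or 28-29 (2 days) can still carry a pre-index PCR. If counting begins the day after, these become 8 days or 1 day. Against day 8, 17 or 10 days remain (16 or 9 if counting begins the day after).

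**4. Expected share of events.** The documents give no delay distribution, so these delays are assumptions. Let K be the PCR-to-event delay in whole days, cut at the look-back limit, with constant incidence. An event on day d has its PCR before day 8 if K > d - 8. Summing P(K > d - 8) over d = 8 to 90 gives the mean of K, so

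share of day 8-90 events = E[K] / 83; share of day 8-365 events = E[K] / 358.

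| Assumed delay | E[K], days | Days 8-90 | Days 8-365 |
|---|---|---|---|
| Death, exponential, mean 7 before the cut | 6.1 | 7.4% | 1.7% |
| Death, exponential, mean 14 before the cut | 9.7 | 11.7% | 2.7% |
| Death, uniform 0-30 | 15.0 | 18.1% | 4.2% |
| Hospitalisation, exponential, mean 3 before the cut | 2.4 | 2.9% | 0.7% |
| Hospitalisation, uniform 0-14 | 7.0 | 8.4% | 2.0% |

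Counting only PCRs before the index date, the uniform delay gives about 9.8% of day 8-90 deaths. A start on day 22 leaves at most about 1.7% of deaths up to day 90, and a start on day 29 about 0.05%.

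**5. Effect on VE, for scale only.** Section 7 quotes a hospitalisation VE of 65.8% for BA.1, a risk ratio of 0.342. Let a share f of unboosted-arm events have an early PCR. The risk ratio becomes 0.342(1 - f) + f if early events are spread equally, and 0.342(1 - f) if they occur only in the unboosted arm.

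- f = 3%: VE 63.8% or 66.8%.
- f = 8%: VE 60.5% or 68.5%.
- f = 2% (upper value by day 365): VE 64.5% or 66.5%.

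The documents give no VE against Covid-19 death, so no such figure is worked for death.

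**The case against.** **The protocol already sees the problem.** Section 9.8 names spill-over from before the index date and plans a later start. That is correct, and it means that the mechanism is not overlooked. But it is a sensitivity analysis for one comparison, and the primary estimates keep the early events.

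**The day 28 start nearly meets its own aim.** A reader might infer from the 30-day window that the planned analysis is badly too short for death. The documents do not support that: section 9.8 aims at events that began before the index date, and a start on day 28 or 29 misses that by two days or one, a negligible share. The gap is material for the day 21 version, and for either version only if day 8 is the target.

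**The effect at day 365 is small.** This stands. Objective 1 is diluted to shares of about 2-4% (death) and 1-2% (hospitalisation).

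**Norway.** A reader might infer that no delayed start could bound the problem there. For hospitalisation this is not established, because the general 14-day/2-day window may apply. For death there is indeed no PCR window, but the cause-of-death definition was chosen for data availability, and imposing a window would change the outcome.

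**4 vs 4 doses.** Both arms are vaccinated on their own index date, so deferral into an unboosted arm cannot arise. Only dilution remains.

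**A PCR date is not an infection date.** A PCR on day 8 may reflect infection on days 0-7, and removing people with a positive PCR on days 0-7 conditions on something after the index date. Both limits stand. The filter narrows the problem without abolishing it.

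**Left to the analysis plan or code?** Dating details often are. Here the protocol itself fixes the start day, the look-back windows and the sensitivity start days, and these do not fit together.

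**Conclusion.** The point holds. As written, the primary analysis admits hospitalisations with a PCR from as early as day -6 and deaths with a PCR from as early as day -22. Neither the eligibility list in section 9.2 nor the prior-infection covariate removes them; the eligibility rows of the target-trial table in section 9.1 should be checked to agree.

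Under constant incidence and the assumed delays, about 7-18% of day 8-90 deaths and 3-8% of day 8-90 hospitalisations would have a PCR before day 8, falling to about 2-4% and 1-2% by day 365. The upper death figure depends on a uniform 0-30 day delay.

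A reader might infer that VE is biased in a known direction. The documents do not settle this: the two mechanisms oppose each other, and deferral of vaccination by infected people is plausible but not stated. The consequence is greatest for the day 8-90 VE and hence the waning estimate, and modest for VE at day 365. The change should be made, because it is cheap and the early interval feeds a primary objective.

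**What to change.** - **Outcomes (9.3).** Where the outcome is PCR-defined, count an event only if its qualifying positive PCR is dated on or after the start of follow-up.
- **Risk set (9.2 and 9.7).** Take out at day 8 every pair in which either member has a positive PCR from day -30 to day 7. At minimum, exclude a positive PCR in the 30 days before the index date.
- **Sensitivity analysis (9.8).** For death, start no earlier than day 30, which clears the index date, and preferably on day 38, which clears day 8. Say whether counting begins on the named day or the day after. Repeat the analysis for the first waning interval.
- **Norway.** Keep the cause-of-death definition. State that the general 14-day/2-day window applies to hospitalisation. Use MSIS test dates only for the pre-day-8 exclusion.

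Cost: a few sentences of protocol text and a date filter plus a pair exclusion in the common scripts, using PCR dates that the countries already hold. Some early events and pairs are lost, which is small against the 3.4 million fourth-dose recipients expected in section 9.5.
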